9.2.3.2. Secondary Efficacy Endpoints

The secondary endpoint for this study is the proportion of participants with clinical response at Week 12 as determined using the mMCS, which will be evaluated in the FAS.

The secondary endpoint will be analyzed using CMH tests stratified by randomization stratification factors (baseline MES [<3 vs 3] and previous use of advanced therapy treatment [advanced therapy-naïve vs advanced therapy-experienced]) for comparison of each MORF-057 dose group with the placebo group, similar to the primary analysis performed for the primary endpoint. The p-values and point estimates of risk difference, along with 95% CIs, will be provided. All participants with missing data for determination of endpoint status will be considered as a non-responder in the analysis.

9.2.3.3. Exploratory Efficacy Endpoints

All proportion-based exploratory efficacy endpoints at Week 12 as defined in Section 3 (e.g., histologic remission or improvement, endoscopic remission or improvement, mucosal healing or improvement, MCS remission or response, UC-related hospitalization or surgery) will be analyzed in the FAS using CMH tests stratified by randomization stratification factors for comparison of each MORF-057 dose group with the placebo group, similar to the primary analysis performed for the primary efficacy endpoint. The p-values will be calculated for the exploratory use. The point estimates of risk difference, along with 95% CIs, will be provided. All participants with missing data for determination of endpoint status will be considered as a non-responder in the analysis.

All the continuous exploratory efficacy endpoints expressed as change from baseline at Week 12 as defined in Section 3 (e.g., non-endoscopic biomarkers of inflammation, PROs) will be analyzed in the FAS using an analysis of covariance model with treatment and randomization stratification factors as factors and baseline values as a covariate. The least-squares means and standard errors with 95% CIs for both changes from baseline in each treatment group and differences between MORF-057 and placebo groups will be provided. P-values will also be calculated for the exploratory use. Participants who do not have the baseline value or the value at Week 12 will be excluded from the analysis.

The time-to-event endpoint (time to symptomatic response) will be analyzed using the stratified Cox regression model with treatment group as an independent variable. The stratification factors include the randomization stratification factors.

All exploratory efficacy endpoints at Week 52 will be summarized descriptively by dose regimens. The participants randomized to the placebo arm at the Induction Period and switched to an active

MORF-057 dose regimen at the Maintenance Period will be summarized separately for the endpoints at Week 52.

[figure not shown]
9.2.3.4. Multiplicity Adjustments

All statistical inference will be 2-sided at a 0.1 level of significance. To control the overall Type I error rate, a hierarchical testing approach as illustrated in [Figure 2](#) will be applied to the statistical testing of the primary and secondary endpoints for comparisons of each MORF-057 dose group with the placebo group.

First, for the primary efficacy endpoint of clinical remission at Week 12, the Hochberg method will be applied to the comparisons of 200 mg B.I.D. with placebo and 100 mg B.I.D. with placebo. If both p-values are <0.1 , both doses will be declared significant. If one of the p-values is ≥ 0.1 , the other p-value will be tested at a 0.05 significance level and the corresponding dose will be declared significant only if the p-value is <0.05 . If both p-values are ≥ 0.1 , no dose will be declared significant, and no further formal testing will be performed.

If both 200 mg B.I.D. and 100 mg B.I.D. achieved the statistical significance for the primary efficacy endpoint, the fixed-sequence method will be used to test the comparison of 100 mg Q.D. with placebo for the primary efficacy endpoint and the comparison of each dose with placebo for the secondary efficacy endpoint of clinical response at Week 12 in a predefined order as specified in [Figure 2](#) below. All tests will be performed at the same significance level $\alpha=0.1$, with the moving to a second test only after a success, i.e., p-value <0.1 , on the previous test. Further testing stops as soon as one test in the sequence fails to meet significance, i.e., p-value ≥ 0.1 .

The testing of the exploratory efficacy endpoints not included in the hierarchical procedure will be used for exploratory purposes only. The details will be specified in the SAP.

Figure 2. Hierarchical Testing Procedure

9.2.4. Safety Analyses

The Safety Population will be used for the summarization of all safety data.

AEs will be coded using the current Medical Dictionary of Regulatory Activities (MedDRA) by System Organ Class (SOC) and Preferred Term (PT), classified from verbatim terms. A TEAE is defined as an AE that occurs between administration of the first dose of study drug and 7 days after the last dose of study drug. TEAEs and TESAEs will be summarized using frequencies and proportions; summaries will be provided for overall and according to SOC and PT. TEAEs leading to study drug discontinuation will be summarized and listed, as appropriate. Summaries of TEAEs will also be presented by severity and relationship (see Section 10.4.3). The duration of TEAEs will be determined and included in listings, along with the action taken and outcome.

Other safety data will include safety laboratory parameters, vital signs, and ECG findings. These data will be summarized with descriptive statistics by absolute values and change from baseline using the Safety Population. The incidence of laboratory abnormalities will be summarized. Worst shift in grade and changes from baseline of the laboratory analytes will be reported. Physical examination findings that are recorded as AEs will be included in those data presentations.

The safety analyses will be performed for the 12-week Induction Period, the 52-week Treatment Period, and the 52-week LTE Period plus the Safety Follow-up Period. In the safety analyses for the 12-week Induction Period, the participants initially randomized into the placebo group and switched to an active MORF-057 regimen after the Week 12 assessments will be analyzed as the placebo group. In the safety analyses for the 52-week Treatment Period and 52-week LTE Period, the placebo recipients switched to an active MORF-057 regimen will be analyzed according to the active MORF-057 regimen they received after Week 12, and their data will be presented separately based on only the safety data collected after the start of the MORF-057 dose.

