To determine time to symptomatic response by Week 12	
 Time to symptomatic response by Week 12 as determined using the Partial mMCS
To assess the effect of MORF-057 on non-endoscopic biomarkers of inflammation at Weeks 12 and 52	
 Change from baseline to Weeks 12 and 52 in high-sensitivity C-reactive protein (hs-CRP) levels Change from baseline to Weeks 12 and 52 in fecal calprotectin levels
To evaluate the effect of MORF-057 on patient-reported outcomes (PROs) at Weeks 12 and 52	
 Change from baseline to Weeks 12 and 52 in Inflammatory Bowel Disease Questionnaire (IBDQ) Score
To evaluate the effect of MORF-057 on corticosteroid-free remission at Week 52	
 Proportion of participants in corticosteroid-free remission at Week 52, as determined using the mMCS, among the participants who were on a stable dose of corticosteroids at baseline
To characterize the effect of MORF-057 on the need for UC-related hospitalizations and surgeries	
 Percentage of participants requiring UC-related hospitalization or surgery at Weeks 12 and 52

Objectives	Endpoints
To evaluate the long-term histologic and endoscopic effects of MORF-057 at Week 104	
 Proportion of participants in histologic remission at Week 104 as determined using the RHI Proportion of participants in histologic remission at Week 104 as determined using the NI Proportion of participants in histologic remission at Week 104 as determined using the Continuous Geboes Score Proportion of participants with histologic improvement at Week 104 as determined using the RHI Proportion of participants with endoscopic improvement at Week 104 as determined using the MES Proportion of participants in endoscopic remission at Week 104 as determined using the MES Proportion of participants in endoscopic remission as determined using the MES and histologic remission as determined using the RHI at Week 104 Proportion of participants with endoscopic improvement as determined using the MES and a histologic improvement as determined using the RHI at Week 104
Safety	
To assess the safety and tolerability of MORF-057	
 Frequencies and proportions for TEAEs, treatment-emergent serious adverse events (TESAEs), and TEAEs leading to study drug discontinuation
Pharmacokinetics (PK)	

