4.1. Overall Design

This study is a randomized, double-blind, placebo-controlled, multicenter, Phase 2b study to evaluate the efficacy and safety of 3 active dose regimens of MORF-057 (as capsule, P.O.) versus matching placebo in study participants with moderately to severely active UC.

Approximately 280 participants will be randomized into the treatment groups in a 1:1:1:1 ratio (i.e., 70 participants per group). The study will enroll participants who are advanced therapy-naïve (i.e., have no previous exposure to an advanced therapy treatment for UC) and advanced therapy-experienced (excluding vedolizumab), with at least 30% but no more than 40% of advanced therapy-experienced participants. Randomization stratification factors will include baseline MES (<3 vs 3) and previous use of advanced therapy treatment (advanced therapy-naïve vs advanced therapy-experienced). All participants will be enrolled from approximately 150 centers worldwide. For this study, moderately to severely active UC will be defined as having an mMCS of 5 to 9 (inclusive), with an MES ≥ 2 (confirmed by central reader).

The main part of this Phase 2b study will consist of a Screening Period (up to 6 weeks, consisting of Stage 1 and Stage 2 testing), a Treatment Period (52 weeks, including a 12-week Induction Period and a 40-week Maintenance Period), and a Safety Follow-up (SFU) Period (4 weeks).

During the main part of this study, there will be approximately 11 scheduled study visits: Screening Visit(s) (Visit 1 at Weeks -6 to -1), multiple Treatment Visits (Visits 2-10 at Weeks 0, 2, 6, 12, 18, 24, 32, 42, and 52 [End of Treatment (EOT)]), and an SFU Visit (visit to occur 4 weeks after the last dose of study drug is received, which will be at Week 56 if the full Treatment Period is completed or earlier if treatment is discontinued early). Study Day 1 represents the first day of the Treatment Period (i.e., when the participant will receive the first dose of study drug).

All participants who complete the 52-week Treatment Period will have the opportunity to continue their treatment in a 52-week Long-Term Extension (LTE) Period.

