Enrolled participants will be randomized to a treatment group to receive active MORF-057 or placebo. Participants initially randomized into an active MORF-057 treatment group will receive an active treatment (according to study period and group assignment) for the full 52-week Treatment Period. Participants initially randomized into the placebo group will be switched to an active MORF-057 regimen (200 mg once a day – evening [Q.D.-E]) after they complete the Induction Period and the Week 12 assessments. After participants complete the full 52-week Treatment Period, they will have the option to enter an additional 52-week LTE Period. All participants who choose to continue in the LTE Period will continue receiving the same MORF-057 regimen they had during the Maintenance Period for up to an additional 52 weeks. However, at Visit 10 or at a scheduled visit in the LTE Period (Visit 11, 12, or 13), if the participant consents, the MORF-057 dose for the LTE Period will be switched to 200 mg B.I.D. If the participant does not consent to the dose switch, they will be allowed to remain on their current LTE Period dose and schedule. The dosing regimens for the 4 treatment groups during the study are shown below.

	Induction Period (12 Weeks)	Maintenance Period (40 Weeks)/ LTE Period (52 Weeks)	LTE Period (52 Weeks)*
Group 1	MORF-057 (200 mg B.I.D.)	MORF-057 (100 mg B.I.D.)	MORF-057 (200 mg B.I.D.)
Group 2	MORF-057 (100 mg B.I.D.)	MORF-057 (100 mg B.I.D.)	MORF-057 (200 mg B.I.D.)
Group 3	MORF-057 (100 mg Q.D.-M)	MORF-057 (100 mg Q.D.-M)	MORF-057 (200 mg B.I.D.)
Group 4	Placebo	MORF-057 (200 mg Q.D.-E)	MORF-057 (200 mg B.I.D.)

Abbreviations: B.I.D., twice a day; LTE, Long-Term Extension; Q.D.-E, once a day (evening); Q.D.-M, once a day (morning).

* Relevant for participants who consent to the dose switch in the LTE Period. For those that do not consent to the dose switch in the LTE Period, they will remain on their current LTE Period dose.

A study schema is provided in [Figure 1](#).

Figure 1. Study Schema

Abbreviations: B.I.D. twice a day; DSFU, Dose Switch Follow-up; EOT, End of Treatment; Q.D.-E, once a day (evening); Q.D.-M, once a day (morning); SFU, Safety Follow-up; UC, ulcerative colitis; V, visit; W, week.

a The SFU Visit will not be performed at Week 56 for participants who enter the LTE Period.

b The assessments to be performed at each visit and the acceptable time windows for each visit are provided in the Schedule of Activities.

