4.2. Scientific Rationale for Study Design

This is a randomized, double-blind, placebo-controlled study. This design will allow for a rigorous evaluation of the safety and efficacy of MORF-057 in participants with moderately to severely active UC.

In the study, 3 active dose regimens of MORF-057 will be compared to placebo for a 12-week Induction Period in order to determine the best overall dosing regimen for future clinical development of MORF-057. This study is the first MORF-057 study with multiple dose arms in UC participants. Multiple B.I.D. doses are being evaluated to compare efficacy, safety, PK parameters, and $\alpha_4\beta_7$ and $\alpha_4\beta_1$ receptor occupancy of MORF-057 B.I.D. administration in UC. An additional Q.D. treatment group is included to compare B.I.D. administration to Q.D. administration. A placebo group is included as a control to compare the efficacy and safety data observed in the active treatment groups to that in a non-active control group. Dose reductions in response to AEs will not be possible due to the double-blind study design; however, study drug interruption will be allowed as deemed necessary by the Investigator and Sponsor Medical Monitor.

In total, the 3 active dose regimens of MORF-057 will be administered for 52 weeks (including a 12-week Induction Period plus a 40-week Maintenance Period). This 52-week design simulates assessment of treatment goals for UC in clinical practice, wherein participants are evaluated for induction of remission, followed by assessment of maintenance of remission over a longer period of time (usually assessed over 52 weeks of continuous treatment in clinical studies). Modern UC clinical trials have Induction Periods lasting 6 to 14 weeks. The 52-week treatment will be followed by an optional 52-week LTE Period. This extension will provide the participants further access to the study drug and collect additional safety and efficacy data up to 104 weeks of exposure.

Participants who are initially randomized to receive placebo will be switched to an active MORF-057 regimen after the 12-week Induction Period. The main purpose for the switch is to collect additional safety data about the active treatment.

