9.3. Analyses for Induction Period, 52-week Treatment Period, and LTE Period

The Treatment Period in the main part of the study includes the 12-week Induction Period and the 40-week Maintenance Period. For the purpose of statistical analyses, the Induction Period and the Maintenance Period will be treated as 2 independent parts. There will be 2 analyses planned: one for the 12-week Induction Period (i.e., the period for the primary efficacy endpoint) and one for the 52-week Treatment Period (i.e., the 12-week Induction Period plus the 40-week Maintenance Period and Safety Follow-up Period). The details of the analyses will be described in the SAP. Additional analysis of the optional 52-week LTE Period for the participants enrolled into the LTE Period will also be performed as appropriate.

Induction Period Analysis

The analysis of the 12-week Induction Period will be performed after all the participants have completed the Week 12 assessments or discontinued the study before the Week 12 assessments. The analysis will formally evaluate the primary and secondary efficacy endpoints, all the exploratory efficacy endpoints defined by Week 12, and safety of MORF-057 vs placebo during

the 12-week Induction Period. The PK and PD data during the 12-week Induction Period will also be summarized.

52-week Treatment Period Analysis

The analysis of the 52-week Treatment Period will be performed after all the participants have completed the Week 52 assessments (and Safety Follow-up Period for participants not rolling over into the LTE Period) or discontinued from the study during the 52-week Treatment Period. The analysis will formally evaluate the efficacy (including all the exploratory efficacy endpoints defined by Week 52), PK, PD, and safety of MORF-057 during the 52-week Treatment Period (and the Safety Follow-up Period for participants not rolling over into the LTE Period). The cumulative data, including those from the Induction Period, will be used in this analysis.

52-week LTE Period Analysis

The analysis of the LTE Period will be performed after all the participants enrolled into the LTE Period have completed the 52-week LTE Period and the Safety Follow-up Period or discontinued the study during the LTE Period. The analysis will evaluate the long-term safety of MORF-057 and selected efficacy endpoints at Week 104 as appropriate during the LTE Period plus the Safety Follow-up Period.

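### In the 52-week safety analysis, crude event percentages cover up to 52 weeks on drug in Groups 1–3 but only about 40 in Group 4, so the two are not comparable without exposure-adjusted rates

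*Protocol*

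**What the plan says.** - **Measure.** Section 3 (repeated in the synopsis) defines the safety endpoint as "Frequencies and proportions for TEAEs, treatment-emergent serious adverse events (TESAEs), and TEAEs leading to study drug discontinuation". Section 9.2.4 says "TEAEs and TESAEs will be summarized using frequencies and proportions". Neither place names a rate per unit of exposure or a common observation window.
- **Windows.** Section 4.1 describes "a Treatment Period (52 weeks, including a 12-week Induction Period and a 40-week Maintenance Period"). Participants randomised to an active group "will receive an active treatment (according to study period and group assignment) for the full 52-week Treatment Period". By contrast, "Participants initially randomized into the placebo group will be switched to an active MORF-057 regimen" (200 mg Q.D.-E) only once Induction and the Week 12 assessments are done.
- **What is counted.** For the 52-week analysis Section 9.3 states "The cumulative data, including those from the Induction Period, will be used in this analysis", so Groups 1–3 contribute events from Week 0. For the former placebo participants Section 9.2.4 says "their data will be presented separately based on only the safety data collected after the start of the MORF-057 dose".
- **Purpose.** Section 4.2 says of the Group 4 switch: "The main purpose for the switch is to collect additional safety data about the active treatment".

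**The concern.** A crude proportion of participants with an event grows with the time they are watched. The 52-week analysis gives Groups 1–3 about 12 more weeks on active drug in which an event can be counted than Group 4 has. Even if all regimens carried exactly the same risk, Group 4's percentages would come out lower. Presenting Group 4 separately prevents pooling but does not equalise the windows.

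The point has some weight because safety data are the stated reason for the switch. The 200 mg Q.D.-E regimen is not given in Induction, so it has no concurrent placebo comparison, and its post-switch data are its only safety information in the main study. A reader will naturally look across to Group 2, which has the same total daily dose of 200 mg split in two (Table 4).

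**Working it through.** **Inputs from the protocol.** Induction is 12 weeks and Maintenance 40 weeks (Section 4.1). Visit 5 is at Day 85 and Visit 10 at Day 365 (Table 1). A TEAE counts up to 7 days after the last dose (Section 9.2.4). There are 70 participants per group (Section 9.5).

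**Assumed, because the protocol gives no figures.** Event incidence, shape of the hazard, and dropout.

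**1. The plan's own windows.** 12 + 40 = 52 weeks, and (365 − 85)/7 = 40.0 weeks. The stated structure reproduces.

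**2. Effect of the window, constant hazard and full follow-up.** If a proportion p has an event over 52 weeks, the same hazard gives q = 1 − (1 − p)^(40/52) over 40 weeks. The relative shortfall is 1 − q/p.

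| 52-week p (Groups 1–3) | 40-week q (Group 4) | Relative shortfall |
|---|---|---|
| 5% | 3.9% | 22.6% |
| 10% | 7.8% | 22.2% |
| 30% | 24.0% | 20.0% |
| 60% | 50.6% | 15.7% |
| 80% | 71.0% | 11.2% |

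For very rare events the shortfall tends to 1 − 40/52 = 23.1%, or 1 − 41/53 = 22.6% with the 7-day tail added to both windows.

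**3. Sensitivity, rare events.**
- Dropout: with assumed annual discontinuation of 10% to 50% in every group, the shortfall goes from 22.2% down to 17.3%.
- Hazard changing with time since first active dose (Weibull shape k): shortfall = 1 − (40/52)^k. This gives 12.3% at k = 0.5, 17.9% at k = 0.75 and 32.5% at k = 1.5.

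**4. Size in participants.** At p = 5%, 70 × 0.05 = 3.5 against 70 × 0.0387 = 2.7, a gap of under one participant. At p = 30% the gap is 6.0 points, against a standard error of the difference of √(0.30 × 0.70/70 + 0.24 × 0.76/70) = 7.5 points.

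**5. What an exposure-adjusted rate does.** Under a constant hazard λ, expected first events divided by expected time at risk equals λ whatever the window. With p = 30%, λ = −ln(0.70) = 0.357, or 35.7 per 100 patient-years (52-week years), in both windows, so the shortfall from window length is zero. If the hazard is not constant, the rate ratio for rare events is (40/52)^(k − 1). At k = 0.5 Group 4's rate is 14% higher, and at k = 1.5 it is 12% lower.

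**The case against.** Several points on the other side are sound.

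- **The exclusion rule is right.** Placebo-period events do not belong in a summary of an active regimen. The difficulty comes only from pairing that rule with crude proportions.
- **No comparison is planned.** The summaries are descriptive, Group 4 is kept apart, and no passage prescribes a table that sets it beside Groups 1–3. The once-daily versus twice-daily comparison that Section 4.2 plans rests on Group 3, which is on active drug for the full 52 weeks. The 12-week Induction safety analysis uses equal windows for all four groups.
- **The SAP may deal with it.** Sections 9 and 9.3 leave analysis detail to the SAP, which is not at hand and could add rates. That softens the point but does not remove it: the protocol itself fixes both the measure and the unequal windows, and a better measure is easily named.

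A reader might infer that the plan makes 200 mg Q.D.-E look up to 23% safer. The documents do not support that. The 23% is a rare-event limit under assumed constant hazard and full follow-up. It is smaller for common events, and where it is largest the absolute gap is under one participant in 70. Section 2.2.2 reports only 5 participants with a serious TEAE and 5 stopping for a TEAE among 280 in the 12-week Induction Period, so window length would be hard to see against chance at such counts.

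A reader might also think that showing Groups 1–3 over their first 40 weeks on drug would make the columns comparable. It would match length only. Group 1 takes 400 mg per day for 12 of those 40 weeks, and Group 4 contains only participants who reached the switch.

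**Conclusion.** The point holds as a limit on comparability. In the 52-week safety analysis, Group 4's crude percentages should not be read against those of Groups 1–3, because they cover about 40 weeks on drug and not up to 52. Under constant hazard and full follow-up, both assumed, window length alone lowers them by about 11% to 23% in relative terms for 52-week incidences from 80% down to rare. The shortfall is smaller with dropout or a falling hazard, and can exceed 23% if the hazard rises with time on drug. Selection of participants who reached Week 12 is a separate matter and is not in these figures. No planned inference is affected, so this is a worthwhile low-cost improvement and not an error that invalidates the analysis.

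**What to change.** In Section 9.2.4 and the matching synopsis text:

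1. For the 52-week analysis, add exposure-adjusted incidence rates for TEAEs, TESAEs and TEAEs leading to study drug discontinuation. Define them as participants with a first event per 100 patient-years at risk on active MORF-057. Keep the frequencies and proportions.
2. Label the Group 4 summary *up to 40 weeks on active drug, participants who reached the Week 12 switch*.
3. Either omit proportions over the first 40 weeks on drug for Groups 1–3 or give them only as a supplementary display, for the confounding noted above.

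**Cost.** A few extra table columns. The dates needed are already collected: treatment start and stop (Section 6.4), first Maintenance dose (Table 1 footnotes) and adverse event onset (Section 8.9). No new data, visits or participants are required. The rates assume a roughly constant hazard, and the text should say so, because a clearly falling or rising hazard would leave a residual difference of the size shown in step 5 of the working.
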